3.1.3 Fast-acting insulin aspart

Fast-acting insulin aspart (faster aspart) (markedet as Fiasp®) is insulin aspart in a new formulation. Faster aspart is being developed with the objective of achieving an increased early absorption of insulin aspart compared to NovoRapid® thereby providing a faster insulin action. Faster aspart aims at approaching the physiological prandial insulin secretion pattern better than currently available treatment and thereby more effectively controlling the PPG excursions and achieving a better PPG control and increased flexibility in the time of dosing around meals compared with NovoRapid®. Results from clinical pharmacology trials in adults comparing pharmacokinetic and pharmacodynamic properties of faster aspart and NovoRapid® have shown that faster aspart resulted in an earlier onset of appearance and a greater early exposure to insulin aspart than NovoRapid® in subjects with T1DM, with the largest difference found within the first 15 minutes after injection. Faster aspart also resulted in a greater early glucose-lowering effect than NovoRapid®, but no statistically significant difference between faster aspart and NovoRapid® in total glucose-lowering effect.

| Protocol | Date: 23 February 2018 | Version: 4.0 | Status: Final | Page: 16 of 112 |

In a therapeutic confirmatory basal-bolus trial in adult subjects with T1DM, faster aspart taken with the meal in combination with Levemir[®] effectively improved glycaemic control and the reduction in HbA_{1c} was statistically significantly larger than with NovoRapid[®]. Mealtime faster aspart provided superior PPG control compared to NovoRapid[®] based on 2-hour PPG increment during a meal test. A statistically significant difference was also demonstrated for 1-hour PPG increment (meal test) in favour of mealtime faster aspart. No statistically significant difference was seen in overall rate of severe or BG confirmed hypoglycaemic episodes between mealtime faster aspart and NovoRapid[®]. The rate during the first one hour after start of a meal, constituting a smaller fraction of all severe or BG confirmed hypoglycaemic episodes, was statistically significantly higher for faster aspart compared to NovoRapid[®]. The overall safety profile for faster aspart and NovoRapid[®] was similar and as expected for insulin aspart.

In a therapeutic confirmatory basal-bolus trial in adult subjects with T2DM, adding and titrating mealtime faster aspart in combination with insulin glargine also effectively improved glycaemic control and non-inferiority to NovoRapid® regarding HbA_{1c} change from baseline was confirmed. A statistically significant benefit in 2-hour PPG increment (meal test) could not be confirmed for faster aspart compared to NovoRapid®. A statistically significant difference was demonstrated for 1-hour PPG increment (meal test) in favour of faster aspart compared to NovoRapid®. No statistically significant difference was seen in overall rate of severe or BG confirmed hypoglycaemic episodes between faster aspart and NovoRapid®. The rate during the first two hours after start of a meal, constituting a small fraction of all severe or BG confirmed hypoglycaemic episodes, was statistically significantly higher for faster aspart compared to NovoRapid®. The overall safety profile for faster aspart and NovoRapid® was similar and as expected for insulin aspart.

The safety profile of faster aspart is expected to be similar to that of NovoRapid[®]. The insulin aspart molecule has a well-known safety profile based on more than 15 years of clinical experience. Compared to NovoRapid[®] faster aspart contains excipients which results in a faster initial absorption of insulin aspart following subcutaneous injection. The added excipients are included in the U.S. Food and Drug Administration's (FDA) list for approved drug products for injections, and no toxicological concerns have been predicted from subcutaneous use in humans at the proposed concentrations. For further details, please refer to the current version of the Fiasp[®] SmPC²¹. If not approved in the country of interest detailed information for faster aspart is available in the current edition of the Investigator's Brochure (IB)²² and any updates hereof.

At the time of this protocol issuance, faster aspart is approved in EU, US and Canada among others.

Protocol
Trial ID: NN1218-4113
CONFIDENTIAL
Version: 23 February 2018 Version: 4.0

CONFIDENTIAL

Final

17 of 112

3.1.4 Insulin degludec

Insulin degludec (marketed as Tresiba®) is a basal insulin with an ultra-long duration of action for once-daily subcutaneous administration at any time of the day, preferably at the same time every day. After subcutaneous injection, soluble and stable multi-hexamers are formed creating a depot of insulin in the subcutaneous tissue. Insulin degludec monomers gradually separate from the multi-hexamers thus resulting in a slow and continuous delivery of insulin degludec into the circulation, leading to the observed ultra-long pharmacokinetic and pharmacodynamic profiles and thereby a flat and stable glucose-lowering effect. The duration of action of insulin degludec is beyond 42 hours within the therapeutic dose range.

For further details please refer to the current version of the Tresiba[®] SmPC 23 . If not approved in the country of interest detailed information for insulin degludec is available in the current edition and any updates of the IB 24 .

At the time of this protocol issuance, insulin degludec is approved in more than 70 countries including US, EU, Canada and Japan.

3.2 Rationale for the trial

The purpose of this trial is to confirm the effect and compare safety of faster aspart compared to NovoRapid® both in combination with insulin degludec with or without metformin in subjects with T2DM treated with a basal-bolus regimen. This trial will provide new information in subjects with T2DM already treated with a basal-bolus regimen as this was not studied in the phase 3a programme.

In the European Medicines Agency (EMA) and FDA note for guidance on clinical investigation of medicinal products for the treatment of diabetes, HbA_{1c} is considered the most widely accepted measure of overall, long-term glucose control. Consequently, HbA_{1c} will be included as the primary endpoint. $\frac{25,26}{100}$

The trial is intended to confirm that administration of faster aspart gives overall glycaemic control non-inferior to NovoRapid[®] and to confirm that faster aspart, with its faster onset of action, is capable of demonstrating superior control of postprandial glucose regulation and excursions as well as a greater reduction in HbA_{1c} in subjects with T2DM.

Protocol
Trial ID: NN1218-4113
UTN: U1111-1180-0636

Date: 23 February 2018 | Novo Nordisk
Version: 4.0
Status: Final

Page:

18 of 112

UTN: U1111-1180-0636 EudraCT no.: 2016-000878-38

4 Objectives and endpoints

4.1 Objectives

Primary objective

To confirm the effect in terms of glycaemic control of treatment with faster aspart compared to NovoRapid[®] both in combination with insulin degludec with or without metformin in adults with T2DM treated with a basal-bolus regimen, using a non-inferiority approach.

Secondary objectives

To confirm superiority of faster aspart compared to NovoRapid[®] both in combination with insulin degludec with or without metformin in adults with T2DM treated with a basal-bolus regimen in terms of:

- Postprandial glucose regulation
- Overall glycaemic control
- Postprandial glucose excursions

To compare the safety of faster aspart to $NovoRapid^{\mathbb{R}}$ both in combination with insulin degludec with or without metformin in adults with T2DM treated with a basal-bolus regimen.

4.2 Endpoints

Baseline is defined as randomisation (Visit 14)

4.2.1 Primary endpoint

Change from baseline in HbA_{1c} 16 weeks after randomisation

4.2.2 Secondary endpoints

4.2.2.1 Confirmatory secondary endpoints

- Change from baseline in 1-hour PPG increment 16 weeks after randomisation (meal test)
- Change from baseline in 1,5-anhydroglucitol 16 weeks after randomisation

Page:

19 of 112

4.2.2.2 Supportive secondary endpoints

Supportive secondary efficacy endpoints

EudraCT no.: 2016-000878-38

- Change from baseline in fasting plasma glucose (FPG) 16 weeks after randomisation
- If a subject achieves HbA_{1c} targets 16 weeks after randomisation:
 - \circ HbA1c < 7.0%
 - o HbA1c < 7.0% without severe hypoglycaemia
- Change from baseline in 30- minutes, 1- hour, 2- hour, 3- hour and 4- hour PPG and 30-minutes, 2- hour, 3- hour and 4- hour PPG increment 16 weeks after randomisation (meal test)
- Change from baseline in endpoints derived from the 7-9-7-point self-measured plasma glucose (SMPG) profile 16 weeks after randomisation:
 - o Mean of the 7-9-7-point profile
 - o Postprandial glucose and PPG increment (mean, breakfast, lunch, main evening meal)
 - o Fluctuation in 7-9-7-point profile
 - o Change in the nocturnal SMPG measurements
- If a subject achieves PPG target (overall mean of daily PPG measurements in 7-9-7-point SMPG profile) 16 weeks after randomisation:
 - o Overall PPG (1 hour) \leq 7.8 mmol/L [140 mg/dL]
 - Overall PPG (1 hour) \(\leq 7.8 \) mmol/L [140 mg/dL] without severe hypoglycaemia
- Insulin dose (Units/day and Units/kg/day; total basal, total bolus and individual meal insulin dose) 16 weeks after randomisation
- Change from baseline in lipids-lipoproteins profile 16 weeks after randomisation (total cholesterol, high density lipoproteins (HDL) cholesterol, low density lipoproteins (LDL) cholesterol)

| Protocol | Date: 23 February 2018 | **Novo Nordisk** | Trial ID: NN1218-4113 | Version: 4.0 | Status: Final |

Page:

20 of 112

Supportive secondary safety endpoints

- Number of treatment emergent adverse events (AEs) during 16 weeks after randomisation
- Number of treatment emergent injection site reactions during 16 weeks after randomisation
- Number of treatment emergent hypoglycaemic episodes classified both according to the ADA definition and Novo Nordisk definition during 16 weeks after randomisation
 - Overall

EudraCT no.: 2016-000878-38

- o Daytime hypoglycaemic episodes
- Nocturnal hypoglycaemic episodes (00:01-05:59 inclusive)
- Hypoglycaemic episodes from start of meal until 1, 2, 4 hours and from 2 hours (exclusive) to 4 hours (inclusive) after start of meal
- Change from baseline in clinical evaluations 16 weeks after randomisation:
 - Physical examination
 - Vital signs (diastolic blood pressure, systolic blood pressure and pulse)
 - Electrocardiogram
 - Fundoscopy/fundus photography
- Change from baseline in central laboratory assessments 16 weeks after randomisation:
 - Haematology (erythrocytes, haematocrit, haemoglobin, leucocytes, thrombocytes)
 - o Biochemistry (alanine aminotransferase (ALT), aspartate aminotransferase (AST), albumin, alkaline phosphatase, creatinine, potassium, sodium, total bilirubin)
- Change from baseline in body weight and body mass index 16 weeks after randomisation

Protocol		Date:	23 February 2018	Novo Nordisk
Trial ID: NN1218-4113	CONFIDENTIAL	Version:	4.0	
UTN: U1111-1180-0636		Status:	Final	

Page:

21 of 112

5 Trial design

EudraCT no.: 2016-000878-38

5.1 Type of trial

This is a phase 3b, 16-week, multicentre, multinational, 1:1 randomised, double-blind, active controlled, treat-to-target, parallel group trial with a 12-week run-in period comparing the effect and safety of faster aspart to NovoRapid[®] both in combination with insulin degludec with or without metformin in subjects with T2DM treated with a basal-bolus regimen.

[figure not shown]

Figure 5–1 Trial Design.

The trial design is summarised in Figure 5–1. The total duration of the trial is approximately 34 weeks divided into the following periods:

- An approximately 2-week screening period
- A 12-week run-in period primarily for optimisation of the basal insulin and subject training
- A 16-week treatment period
- A 30-day follow-up period: FU1; 7 days after end of treatment and FU2; 30 days after end of treatment

The trial includes a screening period followed by weekly visits/phone contacts during the trial. At Visit 2, all eligible subjects will be enrolled in a 12-week run-in period. After the run-in period, subjects eligible for randomisation (HbA_{1c} \leq 9.0% measured at Visit 13) will be randomised (1:1) to receive double blinded treatment with either faster aspart or NovoRapid[®] both in combination with once daily insulin degludec with or without metformin.

Protocol		Date:	23 February 2018	Novo Nordisk
Trial ID: NN1218-4113	CONFIDENTIAL	Version:	4.0	
UTN: U1111-1180-0636		Status:	Final	
EudraCT no.: 2016-000878-38		Page:	22 of 112	

All subjects will have a standardised meal test at baseline (Visit 14 before randomisation) and at end of treatment (Visit 30). The meal test will be described in more details in section 8.3.1.

After the 16-week treatment period, each subject will have a 30-day safety follow-up period.

5.2 Rationale for trial design

The 12-week run-in period has been included to ensure the subjects are being trained in the trial procedures and that the basal insulin titration is optimised. A 16-week treatment period is needed to obtain valid and adequate efficacy and safety data.

The rational for the simple carbohydrate counting (carbohydrate awareness) is to ensure that subjects are able to better control the carbohydrate amount of their meals aiming at a similar carbohydrate intake between days as a supplement to the algorithm based titration.

The rationale for the meal test is to evaluate PPG regulation after a standardised meal when injecting faster aspart compared to NovoRapid[®].

The treat-to-target approach, and thereby the very high frequency of contacts, has been chosen in order to ensure optimal titration of faster aspart and NovoRapid[®].

The 7-day follow-up visit and 30-day follow up contact are introduced in order to collect information on AEs occurring in the follow-up period.

5.2.1 Rational for choice of non-inferiority margin

In a recently finalised faster aspart trial (NN1218-4049, data on file) with a bolus insulin naïve T2DM adult population comparing a basal insulin treatment in addition to metformin to a full basalbolus insulin treatment in addition to metformin the estimated treatment effect in change from baseline HbA_{1c} was - 0.94% [-1.17; -0.72]. In this trial the addition of 3 times daily faster aspart led to a reduction in HbA_{1c} of 1.16% after 18 weeks of treatment. In a similar phase 4 trial $\frac{27}{100}$ investigating the stepwise addition of NovoRapid® to a full basal-bolus regimen in bolus naïve T2DM adults the observed reduction in HbA_{1c} after 21 weeks of treatment was 1.15% (data ANA-3786, data on file) with 3 times daily NovoRapid® added to basal insulin. This gives some indication that the effect of NovoRapid® versus placebo would be close to the 0.94% observed in trial NN1218-4049. Thus using a non-inferiority margin of 0.4%, one of the suggested margins in the FDA guidance²⁶, an improvement of approximately 0.54% would have been preserved using the 0.4% non-inferiority margin.

5.3 **Treatment of subjects**

At Visit 2, all eligible subjects will be enrolled in a run-in period where all subjects will be transferred from their pre-trial basal insulin treatment to insulin degludec once daily. They must

Page:

23 of 112

continue their pre-trial bolus insulin analogue with or without metformin. All OADs, except for metformin must be stopped at Visit 2. For subjects treated with metformin prior to the trial, they should continue with their pre-trial dose of metformin. The dose and dosing frequency of metformin should not be changed at any time during the trial, unless due to safety concerns. Initiation of any other diabetes treatment is not allowed during the screening, run-in or treatment period and must be reported (see section 8.2.6). This includes metformin for subjects not treated with metformin prior to the trial. During the run-in period, the investigator will focus on optimising the basal insulin treatment using a treat-to-target approach following the titration guideline (Appendix A). The bolus insulin will not be titrated during the run-in period unless the investigator finds it necessary to adjust the bolus insulin for safety reasons. All subjects will receive dietary training regarding simple carbohydrate counting (carbohydrate awareness) in the run-in period.

All subjects should consume 3 main meals (breakfast, lunch and dinner) daily throughout the trial.

In the treatment period, eligible subjects must discontinue their pre-trial bolus insulin analogue and will receive double blinded treatment with either faster aspart or NovoRapid® both in combination with once daily insulin degludec with or without metformin. The investigator should focus on optimising the bolus insulin treatment following the bolus dosing algorithm as described in the titration guideline (Appendix A). Surveillance of insulin titration will be performed by Novo Nordisk.

The maximum duration of treatment will be 28 weeks. No maximum dose is specified. Doses are adjusted according to SMPG values (Appendix A).

Use of flash glucose monitoring or a real time continuous glucose monitoring system is not allowed throughout the trial.

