Presentation of results from a statistical analysis will include the estimated mean treatment effects (LSMeans) for change from baseline, if applicable. Estimated mean treatment differences (or ratios) will be presented together with two-sided 95% confidence interval (CI) for all endpoints analysed statistically.

Data collected before randomisation (Visit 14) will only be summarised descriptively.

Testing strategy and estimands

The primary objective of the trial is to confirm the effect of treatment with faster aspart compared to NovoRapid[®], both in combination with insulin degludec with or without metformin in adults with T2DM in terms of glycaemic control, using a non-inferiority approach.

More specifically the upper limit of the 95% confidence interval for the difference between faster aspart and NovoRapid® should be compared to a non-inferiority margin of 0.4%. If it is below or equal to 0.4% non-inferiority will be considered established and effect demonstrated.

The trial also aims to confirm superiority of treatment with faster aspart for a number of secondary confirmatory endpoints. The family-wise type I error rate will be controlled in the strong sense

 Statistical Analysis Plan
 Date:
 12 February 2019
 Novo Nordisk

 Trial ID: NN1218-4113
 Version:
 2.0

 UTN: U1111-1180-0636
 Status:
 Final

 EudraCT No.: 2016-000878-38
 Page:
 7 of 29

using a hierarchical (fixed sequence) testing procedure under the framework of the primary estimand. This is based on a priority ordering of the null-hypotheses, and testing them in this order using the two-sided 95% confidence interval approach until an insignificant result appears. The effect is that rejection of a null hypothesis only will be considered for analyses where all previous null-hypotheses have been rejected in favour of faster aspart.

The steps in the hierarchical testing procedure are as follows:

- Step 1 (Primary analysis): HbA_{1c} non-inferiority of faster aspart versus NovoRapid[®]
- Step 2: 1-hour PPG increment (meal test) superiority of faster aspart versus NovoRapid®
- Step 3: HbA_{1c} superiority of faster aspart versus NovoRapid®
- **Step 4**: 1,5-anhydroglucitol superiority of faster aspart versus NovoRapid[®]

Primary estimand

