2.1 Sample size calculation

The sample size is determined to ensure a sufficient power for step 1 and step 2 in the hierarchical testing procedure for the primary estimand presented in section $\underline{2}$. The power for step 3 and 4 in the hierarchical testing procedure will also be presented. The sample size is determined using a non-inferiority limit of 0.4% in step 1, which was chosen as described in section 5.2.1 in the protocol. The statistical evaluation will be done as described in sections $\underline{2.3}$ and $\underline{2.4}$.

In previous confirmatory trials where faster aspart has been investigated, the completion rates have been high. Therefore it will be expected that treatment discontinuation might be as low as 10% where trial discontinuation constitutes half of these and with similar withdrawal reasons in the treatment arms.

Power for the non-inferiority step (Step 1) is based on a t-statistic under the assumption of a one-sided test of size 2.5% for the FAS. A mean treatment difference of -0.1% for the comparison between faster aspart and NovoRapid[®] in favour of faster aspart is expected. As trials in this population where data from treatment withdrawn subjects is retrieved is limited, a conservative estimate of the standard deviation (SD) in change from baseline in HbA_{1c} of 0.8% was chosen. The power for superiority in step 3 will be calculated using the same assumptions as for step 1 but without the non-inferiority margin.

For determination of power in step 2 in the hierarchical testing, where change from baseline in 1-hour PPG increment 16 weeks after randomisation is compared between faster aspart and NovoRapid® a t-statistic with a two-sided test of size 5% is used, where the treatment difference is

Statistical Analysis Plan		Date:	12 February 2019	Novo Nordisk
Trial ID: NN1218-4113	CONFIDENTIAL	Version:	2.0	
UTN: U1111-1180-0636	CONFIDENTIAL	Status:	Final	
EudraCT No.: 2016-000878-38		Page:	9 of 29	

expected to be at least 0.6 mmol/L [11 mg/dL]. The SD=3.5 mmol/L [63 mg/dL] in change from baseline in 1-hour PPG increments 16 weeks after randomisation based on laboratory analysed PG in a standardised meal test will be considered reasonable based on trials NN1218-3852 and NN1218-3853.

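### Does giving the preserved effect only as 0.54%, and not as 0.32% at the interval limit, weaken the case for the 0.4% margin?

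*Protocol*

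**What the plan says.** Protocol section 5.2.1 takes its historical effect from a trial in bolus-naive adults with type 2 diabetes. That trial compared a full basal-bolus regimen using faster aspart with basal insulin, both with metformin. The estimated effect on change in HbA1c "was - 0.94% [-1.17; -0.72", in a bracket whose confidence level is not given. The section then compares the within-arm reductions in two trials (1.16% with faster aspart, 1.15% with NovoRapid) and takes this as some indication that the NovoRapid effect is near 0.94%.

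The 0.4% margin rests on two supports. It is "one of the suggested margins in the FDA guidance", and "an improvement of approximately 0.54% would have been preserved using the 0.4% non-inferiority margin".

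SAP section 2 (Testing strategy and estimands) compares the upper 95% confidence limit for the difference with that margin: "If it is below or equal to 0.4% non-inferiority will be considered established and effect demonstrated". SAP section 2.1 repeats the margin, "which was chosen as described in section 5.2.1 in the protocol". Neither document states a minimum share of the historical effect that must be kept.

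**The concern.** The margin is compared with a confidence limit of this trial, whereas 0.94% is a point estimate from another trial. Subtracting one from the other gives neither an estimate nor a lower bound for the effect of faster aspart over basal insulin alone. The uncertainty of the historical effect is printed in the same paragraph but left out of the conclusion. With it included, the preserved share at the nearer limit falls below half.

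This trial has no basal-only arm, so the size of effect behind the words about demonstrated effect can come only from section 5.2.1. The historical effect also comes from bolus-naive subjects, while protocol section 3.2 says this trial adds information on subjects "already treated with a basal-bolus regimen as this was not studied in the phase 3a programme". If a reader took 0.54% as the least effect that a pass guarantees, the benefit would be overstated. If the nearer limit had fallen below 0.4%, the margin itself would have been in doubt.

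**Working it through.** **Inputs.** Historical effect 0.94%, with limits 0.72% and 1.17% (protocol 5.2.1). Margin 0.40% (protocol 5.2.1; SAP 2 and 2.1). SD of change 0.8%, 536 subjects per arm, planned difference −0.1% (SAP 2.1).

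**Step 1: the plan's own figure.** Preserved effect = historical effect − margin; preserved share = preserved effect / historical effect.

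| Historical effect | Preserved | Share kept |
|---|---|---|
| 0.94 (point estimate) | 0.94 − 0.40 = 0.54% | 0.54/0.94 = 57% |
| 0.72 (nearer limit) | 0.72 − 0.40 = 0.32% | 0.32/0.72 = 44% |
| 1.17 (farther limit) | 1.17 − 0.40 = 0.77% | 0.77/1.17 = 66% |

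The stated 0.54% is reproduced exactly. The margin lies below all three values of the historical effect.

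**Step 2: how strict 0.32% is.** It sets the worst limit of one trial against the worst limit of the other. Combining the two errors instead, and assuming that the bracket is a 95% interval:

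- Historical SE = (1.17 − 0.72)/3.92 = 0.115.
- Trial SE = 0.8 × √(2/536) = 0.0489; half-width = 1.96 × 0.0489 = 0.096.
- Bare pass (upper limit exactly 0.40): observed difference = 0.40 − 0.096 = 0.304.
- Indirect effect over basal insulin = 0.94 − 0.304 = 0.636, or 0.64%.
- Combined SE = √(0.115² + 0.0489²) = 0.125; 95% interval 0.39% to 0.88%.

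So 0.54% lies below the indirect estimate and inside its interval, even at the poorest result that still passes. Retention of half of 0.94 (that is, 0.47) can be tested at the same point: (0.304 − 0.47)/√(0.0489² + 0.25 × 0.115²) = −2.20, one-sided p = 0.014.

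**Step 3: how likely a bare pass is under the plan.** An observed +0.304 lies (0.304 + 0.1)/0.0489 ≈ 8 standard errors from the planned −0.1. At an observed −0.1 the upper limit is −0.1 + 0.096 = −0.004, and even the nearer historical limit then leaves 0.72 + 0.004 ≈ 0.72%.

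**Step 4: does anything in the plan depend on the figure?** Step 1 power is approximately Φ((margin − true difference)/0.0489 − 1.96). With margin 0.40 and true difference −0.1 it exceeds 99.9%, as stated. For illustration only, a margin of 0.36 (half of 0.72) or 0.30 also gives more than 99.9%, at a true difference of −0.1 or 0. The sample size is driven by Step 2 (80.1% power), which does not involve the margin.

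**The case for a change.** The strongest case for a change is that section 5.2.1 is the only place in either document that puts a size on the effect behind a pass, and that it uses the more favourable of two figures available in the same paragraph. One added clause would supply the other, at almost no cost. The historical effect is also carried across two gaps, from faster aspart to NovoRapid and from bolus-naive to basal-bolus subjects, and 0.32% makes no allowance for either.

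The arithmetic stands: 0.32% (44%) is correct, it is not stated, and it does not need the bracket to be a 95% interval. The rest carries less weight:

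- Section 5.2.1 explains the choice of margin. It does not say that a pass guarantees 0.54%, and the decision rule speaks of demonstrated effect without a size. The figure is therefore too favourable only if read as a lower confidence limit, which the text does not claim.
- The 0.39% lower limit above is not a figure from the documents. It needs an assumed 95% level, the planning SD and sample size, and a hypothetical observed difference of +0.304.
- The population gap is open to view. Section 5.2.1 says that the earlier subjects were bolus-naive, and section 3.2 gives the unstudied population as a reason for the trial. The documents do not show whether the effect is larger or smaller there, so no direction of bias follows.

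**Conclusion.** No change is needed. Section 5.2.1 reports the preserved effect at the point estimate (0.54%, 57%) and leaves the reader to make the same subtraction at the nearer limit (0.32%, 44%). This is an incomplete rationale, not a wrong figure, and the interval needed to complete it is in the same paragraph.

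The margin stays below the nearer limit of the historical effect (0.40 against 0.72), which is the check that would have mattered. No document sets a retention threshold that 44% would fail. Hypotheses, decision rule, sample size, power and conclusion depend on 0.4% alone. An author revising the section for other reasons could label the bracket and add the 0.32%, but nothing in the conduct or analysis turns on it.

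The conclusion assumes, as the protocol does, that the NovoRapid effect is close to the one observed with faster aspart and carries over to subjects already on basal-bolus treatment. Only the combined-error figures also assume that the bracket is a 95% interval. The cited guidance and the data on file were not available, so whether they address the interval limit is not known.
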